# 1. SYNOPSIS

| Title                      | Incidence of Postoperative Residual Neuromuscular Blockade - A Multicenter,
Observational Study in Portugal.  |  |  |
|----------------------------|--|--|--|
| Study Design               | Epidemiological multicenter, observational, prospective study.   |  |  |
| Primary
Objective       | To determine the incidence of postoperative residual neuromuscular blockade - defined by a TOF ratio < 0.9 - at PACU arrival.  |  |  |
| Secondary
Objectives    | To determine the incidence of severe postoperative residual neuromuscular blockade
– defined by a TOF ratio < 0.7 at PACU arrival   |  |  |
|                            | To evaluate the association of postoperative residual blockade and the use of reversal agents (neostigmine, sugammadex or none)  |  |  |
|                            | To evaluate the association of postoperative residual blockade and the use of intra-
operative monitoring of neuromuscular blockade   |  |  |
| Target
Population       | Subjects aged at least 18 years old (n=360) admitted for different types of elective surgical procedures requiring general anesthesia with neuromuscular blocking agents.  |  |  |
| Sample Size
Calculation | 
 
Sample size was calculated according to the following assumptions:
 
Portuguese population to be submitted to surgery with general anesthesia in the next year is approximately 100.000 cases
 
incidence of patients that arrive at the PACU with objective evidence of incomplete neuromuscular recovery is 26%
 
Discontinuation rate of 20%
 
Assuming a margin of error of 5% and a confidence interval of 95%, it is expected that approximately 360 patients are required to achieve primary endpoint
 
 |  |  |
| Statistical
Analysis    | Patients will be stratified as follows: patients with TOF ratio $\geq$ 0.9, patients with TOF ratio < 0.9, patients with TOF ratio < 0.7   |  |  |
|                            | Absolute and relative frequencies will be calculated for each category of TOF ratios.
95% confidence intervals will be estimated and presented.   |  |  |
|                            | Statistical significance of the comparisons with TOF ratio <0.9 and TOF ratio <0.7 at PACU will be performed through Chi-square test or Fisher's Exact Test. In addition, relative risks and 95% CI for TOF ratio <0.7 and TOF ratio <0.9 at PACU will be performed for the comparisons.   |  |  |

A descriptive analysis will be performed for all demographic and clinical data.

# 1.1. Study Flow Chart

|  | Pre-
surgery           | Post-surgery                       |  |
|--|---------------------------|------------------------------------|--|
| Procedures   | At
Anesthetic
visit | Period 1
At PACU arrival | Period 2
At hospital discharge |
| Written informed consent   | x                         |                                    |  |
| Inclusion/exclusion criteria   | x                         | x                                  |  |
| Patient number   |                           | x                                  |  |
| Vital signs: arterial blood, pressure,
heart rate, temperature and oxygen
saturation |                           | x                                  |  |
| Neuromuscular blockade assessment
(TOF ratio measurements)                              |                           | x                                  |  |
| Demographic data (gender, age,
weight, height)  |                           | x                                  |  |
| Clinical history   |                           | x                                  |  |
| Co-morbidities   |                           | x                                  |  |
| Information about operating room   |                           | x                                  |  |
| Surgical diagnostic  |                           | x                                  |  |
| ASA status   |                           | х                                  |  |
| Medication: NMBA, NMBA reversal agents, volatile anesthetics, hypnotics, opioids           |                           | x                                  |  |
| Dates: discharge/death   |                           | x                                  |  |
| Adverse events   |                           |                                    | x  |
| Final outcome: discharge/death   |                           |                                    | x  |

# 3. LIST OF ABBREVIATIONS

| Abbreviation | Definition                                |
|--------------|---|
| AE           | Adverse Event                             |
| ASA          | American Society of Anesthesiologists     |
| CNPD         | National Data Protection Committee        |
| CRF          | Case Report Form                          |
| CSR          | Clinical Study Report                     |
| FAS          | Full Analysis Set                         |
| ICH          | International Conference on Harmonization |
| ICF          | Informed Consent Form                     |
| IEC          | Independent Ethics Committee              |
| IRB          | Institutional Review Board                |
| NA, N/A      | Not Applicable                            |
| NMB          | Neuromuscular Blockade                    |
| NMBA         | Neuromuscular Blocking Agent              |
| OR           | Operating Room                            |
| PACU         | Post Anesthesia Care Unit                 |
| SAE          | Serious Adverse Event                     |
| TOF          | Train-of-four                             |

# 4. RATIONALE

General anesthesia is usually achieved through the balance of three components: analgesic, hypnotic and neuromuscular blocking agents (NMBAs). NMBAs optimize surgical conditions and tracheal intubation. Nevertheless, one of the problems associated is the residual neuromuscular blockade, secondary to the remaining effect of these agents at a moment that complete reversal of their effect would be desirable.

Residual neuromuscular blockade is frequently described in surgical patients at the post anesthesia care units (PACUs) when non-depolarizing NMBAs are administered in the operating room (OR). Incidence values range from 16% to more than 70% with a definition of residual neuromuscular blockade in presence of train-of-four (TOF) ratio < 0.7-0.9. The use of NMBAs of intermediate action, intraoperative neuromuscular monitoring and reversal of NMBAs have been described as factors that contribute to the reduction, but not the elimination, of residual neuromuscular blockade.

Quantitative neuromuscular monitoring methods, such as acceleromyography, are the most reliable to assess neuromuscular blockade.8,15 Quantitative neuromuscular monitoring provides a more objective data on neuromuscular transmission and improves detection of residual neuromuscular blockade in comparison with visual or tactile evaluation of the TOF response.

For many years, the standard criterion of adequate recovery of neuromuscular function was a TOF ratio of at least 0.7. However, evidences have been provided that considerable signs and symptoms of residual neuromuscular blockade may persist until a TOF ratio of 0.9. Therefore, presently, the criterion for adequate reversal of residual neuromuscular blockade is a TOF ratio  $\geq$  0.9 at the thumb adductor.

Clinical consequences of residual neuromuscular blockade in PACUs have been documented since 1979. Impaired airway protective reflexes and increased risk for aspiration, a reduced hypoxic ventilator response, pharyngeal dysfunction, hypoxemia, diplopia and unpleasant symptoms of muscle weakness are complications of residual neuromuscular blockade that may increase postoperative morbidity.

A first study was conducted in eight Portuguese hospitals between July and November 2010 reported a global incidence of 26% of TOF ratio < 0.9 at arrival at the PACU highlighting the dimension of the problem in Portugal.

Since 2010 neuromuscular blockade management had considerably changed. This previous study promoted a growing conscience of the real importance of residual blockade in our surgical patients and convinced us that changes must be done to improve these results. Clinical sessions on neuromuscular blockade management and monitoring were held in various Portuguese hospitals. At the same time, a novel neuromuscular reversal agent (sugammadex) was available and experience with this new drug has been increasing each year replacing in many cases the conventional anticholinesterasic drugs. Based on these two facts we propose to reassess the incidence of residual neuromuscular blockade six years after the first study keeping a similar study design to confirm the paradigm shift that we believe might have happened.

# 5. OBJECTIVES

## 5.1. Primary Objective

 $_{\odot}$  To determine the incidence of postoperative residual neuromuscular blockade - defined by a TOF ratio < 0.9 - at PACU arrival.

## 5.2. Secondary Objective

- To determine the incidence of severe postoperative residual neuromuscular blockade
   defined by a TOF ratio < 0.7 at PACU arrival

- To evaluate the association of postoperative residual blockade and the use of reversal agents (neostigmine, sugammadex or none)
- To evaluate the association of postoperative residual blockade and the use of intraoperative monitoring of neuromuscular blockade

## 5.3. Exploratory Objective

 $_{\odot}$  To evaluate the association of postoperative residual blockade with comorbidities and ASA status

# 6. INVESTIGATIONAL AND ANALYSIS PLAN

### 6.1. Overall Study Design

This is a multicenter, observational/non-interventional study involving adult patients undergoing different types of elective surgical procedures requiring general anesthesia with neuromuscular blocking agents.

The study will have two periods:

- Period 1 Evaluation at PACU arrival.
- Period 2 Collection of hospital patient discharge data.

A total of 360 patients will be included from approximately 10 centers in Portugal, where the PACU is adjacent to the Operating Room (OR). Each center should recruit between 30 and 40 patients.

### 6.2. Beginning and End of the Study

Each subject is considered to be enrolled in the study when the subject has provided written informed consent.

Enrolment will be stopped when approximately 360 patients are recruited.

A subject is considered to have completed the trial after all of the protocol specified activities are completed.

A subject is considered to have discontinued after he/she has withdrawn consent or has been discontinued under the conditions specified in Section 6.4.3.

Overall, study start is when the first site is initiated and study ends at database lock.

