### 6.3. Study Procedures

During the routine preoperative anesthesia visit the patient will be asked to participate in the study. A description of the study will be provided to the patient by the investigator or qualified designee and any questions will be properly answered. If the patient agrees to participate in the study an informed consent form (ICF) will be signed.

Consent must be documented by the subject's dated signature or by the subject's legally acceptable representative's dated signature on a consent form along with the dated signature of the person conducting the consent discussion. A copy of the signed and dated consent form should be given to the subject before participation in the study.

The initial informed consent form, any subsequent revised written informed consent form and any written information provided to the subject must receive the IRB/ERC's approval/favorable opinion in advance of use. The subject or his/her legally acceptable representative should be informed in a timely manner if new information becomes available that may be relevant to the subject's willingness to continue participation in the study.

All consented subjects will be given a unique patient number that will be used to identify the subject for all procedures. Each subject will be assigned only one patient number.

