#### Neuromuscular blockade evaluation

Neuromuscular blockade will be evaluated using a quantitative method. Three consecutive TOF stimulations will be applied. In case these 3 measures differ more than 20%, another

sequence of 3 consecutive TOF measurements will be considered. If after the 2nd sequence the 3 consecutive TOF measurements still differ more than 20% between the maximum and the minimum the patient will be excluded.

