## 6.4. Target Population

### 6.4.1. Subject Inclusion Criteria

To participate in this study subjects must meet the following criteria:

- 18 years of age or older;
- Informed consent signed;
- Admission for elective surgery;
- Administration of non-depolarizing NMBAs during surgery.

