### 6.4.2. Subject Exclusion Criteria

Subjects will be excluded from this study if they do not fulfill the inclusion criteria or in case of:

- Admission for emergency surgery;
- Reoperation on the same hospital admission;
- More than 10 minutes elapsed between extubation and neuromuscular block monitoring at PACU.

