# 7. STATISTICAL ANALYSIS

## 7.1. Sample size determination

Sample size determination was calculated by assuming that the Portuguese population to be submitted to elective surgery with general anesthesia is approximately 100.000 cases/year.

From the previous study of [name] et al, the incidence of patients that arrive at the post anesthesia care unit with objective evidence of incomplete neuromuscular recovery was 26%.

When considering this incidence of 26%, a margin of error of 5% (acceptable maximum deviation) and a confidence interval of 95%, we obtained a minimum sample size of 295 patients (StatsDirect 3 Statistical Software).

Considering conservative estimation for the discontinuation rate of 20%, it is expected that approximately 360 patients are required to achieve the primary endpoint.

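### The target of 360 appears to count preoperative consents, but two eligibility criteria can be confirmed only later, and the 20% allowance neither covers failed eligibility nor leaves the stated minimum of 295

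*Combined protocol and SAP*

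**What the plan says.** **Counting point.** Section 6.2 says "Each subject is considered to be enrolled in the study when the subject has provided written informed consent" and "Enrolment will be stopped when approximately 360 patients are recruited". Section 6.3 fixes the time of consent: "During the routine preoperative anesthesia visit the patient will be asked to participate in the study". Section 6.1 speaks of 360 patients being included, from about 10 centers with 30 to 40 each. The plan does not define *recruited* or *included* separately from *enrolled*.

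**Criteria settled after consent.** Section 6.4.1 requires "Administration of non-depolarizing NMBAs during surgery". Section 6.4.2 excludes a patient if "More than 10 minutes elapsed between extubation and neuromuscular block monitoring at PACU". The flow chart in Section 1.1 lists the criteria at the anesthetic visit and again at PACU arrival. The neuromuscular blockade evaluation text under Section 6.3.1 adds a further removal: if, after a second sequence, the three "measurements still differ more than 20% between the maximum and the minimum the patient will be excluded".

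**Analysis set and allowance.** The FAS (Section 7.7) admits only patients who meet all criteria. Section 7.1 derives a minimum of 295 and moves to approximately 360, "Considering conservative estimation for the discontinuation rate of 20" per cent. Section 6.2 limits discontinuation to withdrawal of consent or the conditions of Section 6.4.3, where the one listed condition is that three TOF measures cannot be obtained.

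**Patient number.** Section 6.3 says "All consented subjects will be given a unique patient number". The flow chart marks the patient number at PACU arrival.

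**The concern.** The sample size is a precision calculation, so what matters is how many patients reach the FAS. On the plain wording of Section 6.2, a patient takes a place at consent, before it is known whether a non-depolarizing NMBA will be given or whether the TOF reading will fall inside the 10-minute window. A patient who fails either criterion has been enrolled but cannot be analysed. The only allowance for loss is tied to a definition of discontinuation that does not mention failed eligibility, and no replacement rule is given.

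At stake are the number behind the primary estimate, and hence the 5-point margin, and the reader's ability to follow patients from consent to analysis. The two statements about the patient number add to the second problem, because centers could count toward their 30 to 40 at different moments.

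**Working it through.** **Inputs.** From Section 7.1: incidence p = 0.26, margin d = 0.05, 95% confidence (z = 1.96), population N = 100,000, minimum 295, discontinuation 20%, target approximately 360. The share s of consented patients later found ineligible is not in the documents. It is assumed here, over 0% to 20%.

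**1. Reproduce the plan's figure.**
- n0 = z² p(1 − p)/d² = 1.96² × 0.26 × 0.74/0.05² = 295.6
- With finite population correction: n = n0/(1 + (n0 − 1)/N) = 294.8, which rounds up to 295. This matches Section 7.1.

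**2. Check the step to 360.**
- Dividing by the retained fraction: 295/0.80 = 368.75, so 369.
- Multiplying by 1.20: 295 × 1.20 = 354.
- The stated figure lies between the two. Section 7.1 does not show which was used.
- Read forward, 360 × 0.80 = 288, which is 7 short of 295 before any ineligibility.

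**3. Add ineligibility to the planned 20% discontinuation.** Evaluable number = 360 × (1 − s) × 0.80. Half-width = 1.96 × √(0.26 × 0.74/evaluable). The finite population correction is left out here; it changes the half-width by about 0.01 point or less.

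| Assumed s | Evaluable | Half-width (points) | Increase over s = 0 | Consents needed for 295 |
|---|---|---|---|---|
| 0% | 288 | 5.07 | – | 369 |
| 5% | 274 | 5.20 | 0.13 | 389 |
| 10% | 259 | 5.34 | 0.27 | 410 |
| 20% | 230 | 5.66 | 0.59 | 461 |

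The last column is 295/((1 − s) × 0.80), rounded up.

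**4. Total loss that 360 consents can bear.** 1 − 295/360 = 65/360, or about 18.1% from all causes.
- With 10% discontinuation, tolerable ineligibility is 1 − 295/(360 × 0.90) = 9.0%.
- With 5% discontinuation, it is 1 − 295/(360 × 0.95) = 13.7%.
- With the planned 20%, there is no room at all.

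**The case against.** The strongest reply is that nothing shows places being lost. Section 6.1 speaks of 360 patients included, Section 6.4.2 removes ineligible subjects from the study, and the flow chart re-checks criteria at PACU arrival. One can therefore read 360 as patients who passed that check. The target is approximate, and 30 to 40 patients at about 10 centers gives 300 to 400, so 360 consents is not a hard cap. This stands as an alternative reading. It does not remove the problem, because Section 6.2 ties enrolment to consent and stops enrolment at 360 without saying which count applies.

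The second reply is that Section 7.1 calls the 20% conservative, and it may have been meant to cover every loss between consent and analysis. That is possible, though the text does not say so. Even then, 288 remain, not 295.

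Three stronger readings are tempting, and the documents do not support them.
- A reader might infer that ineligibility is what pushes the study below 295. The first 7 patients of the shortfall come from the 20% alone. Moreover, 295 is still reached if total loss stays within about 18.1%.
- A reader might infer that both criteria are unknown until PACU arrival. NMBA use is known in the operating room. It is also largely foreseeable, since the target population is patients whose procedures require general anesthesia with these agents.
- A reader might infer that patients lost before the PACU cannot be traced. Section 9.1.1 requires signed consent forms to be kept, so the number consented is recoverable, and Section 6.4.3 requires the reason and date of withdrawal on the CRF. What the plan lacks is a required record of why a consented patient proved ineligible.

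The flow chart is also weak evidence of intended numbering practice. The same column marks discharge and death dates at PACU arrival, so the placement of its marks may be unreliable.

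**Conclusion.** The point holds as a mismatch between the unit counted in Section 6.2, the allowance in Section 7.1 and the patients admitted to the FAS.

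If 360 means consents, the plan's own 20% gives 288 evaluable patients and a half-width of 5.07 points, not 295 and 5.0. This needs no outside assumption. If ineligibility comes on top of the full 20%, the half-width is 5.2 to 5.7 points for an assumed 5% to 20%. That range illustrates sensitivity and is not a forecast, since the documents give no rate.

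The consequence is a modest loss of precision. The counting rule does not alter who qualifies for the FAS, so it does not bias the incidence estimate. The disagreement between Section 6.3 and the flow chart over when the patient number is given needs reconciling whatever the loss rate. It does not show that centers would in fact follow different rules.

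**What to change.** 1. **Define the count.** In Section 6.2, state that the target of 360 and the center quota of 30 to 40 count patients whose eligibility is confirmed at PACU arrival. Ineligibility then no longer reduces the number. A full 20% discontinuation among those counted would still leave 288, so Section 7.1 should show that figure.

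   Alternatively, keep 360 consents. In that case, say in Section 7.1 that the allowance covers all losses from consent to the FAS, and restate what this delivers: 288 patients and about 5.1 points at 20% total loss, with fewer patients and a wider margin if ineligibility is added.
2. **Reconcile the patient number.** Make Section 6.3 and the flow chart agree by numbering at consent, and record the reason for each later ineligibility. Consented, ineligible, discontinued and analysed patients can then be reported separately.

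A rule that stops the study at 295 valid TOF results is not recommended. It would conflict with a quota of 30 to 40 at about 10 centers (300 to 400 patients) and would need a running central count.

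The cost is wording in Sections 6.2, 6.3, 7.1 and the flow chart and a short record of ineligibility reasons, plus either some extra consent discussions or a slightly less favourable stated margin.

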### 6.3. Study Procedures

During the routine preoperative anesthesia visit the patient will be asked to participate in the study. A description of the study will be provided to the patient by the investigator or qualified designee and any questions will be properly answered. If the patient agrees to participate in the study an informed consent form (ICF) will be signed.

Consent must be documented by the subject's dated signature or by the subject's legally acceptable representative's dated signature on a consent form along with the dated signature of the person conducting the consent discussion. A copy of the signed and dated consent form should be given to the subject before participation in the study.

The initial informed consent form, any subsequent revised written informed consent form and any written information provided to the subject must receive the IRB/ERC's approval/favorable opinion in advance of use. The subject or his/her legally acceptable representative should be informed in a timely manner if new information becomes available that may be relevant to the subject's willingness to continue participation in the study.

All consented subjects will be given a unique patient number that will be used to identify the subject for all procedures. Each subject will be assigned only one patient number.

